NA-IAO	Non-Acute Intracranial Artery Occlusion
NIHSS	National Institute of Health Stroke Scale
OR	Odds Ratio
pc-ASPECTS	Posterior Circulation Alberta Stroke Program Early CT Score
PH1	Parenchymal Hemorrhage 1
PH2	Parenchymal Hemorrhage 2
PMI	Pons-Midbrain Index
PSM	Propensity Score Matching
PT	Prothrombin Time
PWI	Perfusion Weighted Imaging
RAPID	Rapid Processing of Perfusion and Diffusion
RIH	Ischemic Field
SAE	Serious Adverse Event
SAH	Subarachnoid Hemorrhage
SD	Standard Deviation
sICH	Symptomatic Intracranial Hemorrhage
sNA-IAO	Symptomatic Non-Acute Intracranial Artery Occlusion
TIA	Transient Ischemic Attack
TT	Thrombin Time
VA	Vertebral Artery

Protocol Synopsis

Title	Endovascular Recanalization vs Medical Treatment for Non-Acute Intracranial Artery Occlusion (ERNA-IAO): A Multicenter, Prospective, Cohort Study
Sponsor	Beijing Tiantan Hospital, Capital Medical University
Study period	Enrollment from January 1, 2020 to October 31, 2023 (and 1 year follow-up)
Study Centers	
Interventional Neuroradiology, Department of Neurology, Beijing Tiantan Hospital, Capital Medical University;
 
Department of Neurology, Beijing Liangxiang Hospital;
 
Department of Neurointerventional Radiology, Beijing Fengtai You'anmen Hospital;
 
Department of Neurology, Ordos Central Hospital;
 
Department of Neurology, Jingjiang People's Hospital Affiliated to Yangzhou University;
 
Department of Neurology, Taizhou first people's Hospital.

Study Objectives	The primary objective of this study is to investigate whether endovascular recanalisation (ER) plus medical treatment is superior to medical treatment alone for symptomatic non-acute intracranial artery occlusion (sNA-IAO) in the primary outcome.
Study Design	multicenter, prospective, cohort study
Study Population	Patients with sNA-IAO, with the time from the latest ischemic event (ischemic stroke or transient ischemic attack) in the territory of the qualifying artery to enrollment being beyond 24 hours and within 90 days, as confirmed by computed tomography angiography (CTA) or digital subtraction angiography (DSA).
Inclusion Criteria	
 • (1) Age ranging between 18 and 80 years. • (2) sNA-IAO defined as: 
 ① Time from latest ischemic event (ischemic stroke or TIA) in territory of the qualifying artery to enrollment is beyond 24 hours and within 90 days. ② Occlusion of intracranial internal carotid artery, M1 segment of middle cerebral artery, intracranial vertebral artery (with contralateral vertebral artery hypoplasia or occlusion) or basilar artery confirmed by computed CTA or DSA. • (3) Computed tomographic (CT) or magnetic resonance imaging (MRI) demonstrating ASPECTS ≥ 6 (for anterior circulation), or pc-ASPECTS ≥ 6 and

[figure not shown]
	
pons-midbrain index (PMI) <3 (for posterior circulation).
 
 • (4) Modified Rankin Scale (mRS) score 0-2 at the time of enrollment. • (5) Technical feasibility of endovascular recanalization for the qualifying artery evaluated by two experienced interventional neuroradiologists. • (6) More than one risk factor for atherosclerosis. • (7) Signed informed consent form.
Exclusion Criteria	
 • (1) Severe stenosis or occlusion of other arteries, or tandem stenosis proximal to the qualifying artery. • (2) Intracranial hemorrhagic diseases such as definite Intracranial tumors, any intracranial vascular malformations, hemorrhagic transformation of infarction, spontaneous intracranial hemorrhage (cerebral parenchymal, subarachnoid, subdural, or epidural) within 30 days. • (3) Non atherosclerotic intracranial arterial disease: arterial dissection, moyamoya disease or moyamoya syndrome demonstrated by imaging examination, or a definite medical history of autoimmune vasculitis. • (4) Evidence of cardioembolic embolism such as atrial fibrillation, prosthetic valve(s), infective endocarditis, mitral stenosis, atrial myxoma, intracardiac clot or vegetation, left ventricular aneurysms and so on. • (5) Known unstable angina or myocardial infarction within the last 6 months. • (6) Intolerance or allergic reaction to any treatment-related medication, including aspirin, clopidogrel, heparin, and local or general anesthetics. • (7) History of life-threatening allergy to contrast dye. • (8) Severe liver impairment (AST or ALT > 3 times normal, cirrhosis), serum creatinine > 3.0 mg/dl. • (9) Past history of EC-IC bypass surgery or EVT. • (10) Major surgery (including open femoral, aortic, or carotid surgery) within previous 30 days or planned in the next 90 days after enrollment. • (11) Late-stage malignant tumors, cachexia, or other serious diseases and an expected life expectancy of less than 1 year. • (12) Pregnant, perinatal stage or lactating women.
Treatments and Study Groups	
The technical feasibility of ER for all sNA-IAO patients in this study will be collaboratively evaluated by two experienced interventional neuroradiologists. The decision to select either medical treatment alone or additional ER is made by the patients themselves or their legal representatives. Patients are subsequently divided into two groups based on selection of treatment approach: the medical group and the ER group.

Follow-up schedule	Baseline, 30±7 days, 90±7 days, 1 year±30 days
Primary Outcome	
The primary outcome is a composite outcome as follows:
 
 • Any stroke or death within 30 days after enrollment • Ischemic stroke in the territory of the qualifying artery from 30 days to 1 year after enrollment.
Secondary Endpoints	
Secondary outcomes as follows:
 
 • Mortality within 1 year; • Ischemic stroke outside the territory of the qualifying artery within 1 year; • Disabling stroke within 1 year; • TIA in the territory of the qualifying artery within 1 year; • Unplanned revascularization (EC-IC bypass surgery or ER) of the qualifying artery within 1 year; • Myocardial infarction within 1 year; • Composite vascular events within 1 year, including any stroke, myocardial infarction, and unplanned revascularization; • Quality of life assessment (EuroQol-5-Dimensions scale questionnaire) at 1 year; • mRS score at 1 year; • Periprocedural outcomes; • Restenosis or reocclusion (symptomatic or asymptomatic).
Statistical Methods	
 • Categorical variables will be compared between treatment groups using χ^2 or Fisher's exact test. Continuous variables or ordinal variables will be compared between treatment groups using t-test or Wilcoxon-Mann-Whitney test. • The primary and time-to-event secondary outcomes will be compared between the groups using log-rank test. • Kaplan-Meier curves will be used to show the incidence of outcomes over time. • The hazard ratio (HR) and adjusted hazard ratio (aHR) between groups, along with their 95% CIs, will be determined using univariate and multivariate Cox proportional hazards regression models. • Propensity score matching (PSM) will be performed to reduce the possible influence of selection bias and confounders on the outcomes. • A 2-sided P value less than 0.05 is considered to demonstrate a statistically significant difference. • All analyses will be performed with using SAS Version 9.4.

Schedule of assessments

Table 1: Summary of Study Treatment and Study Assessments

Study Requirements	Screening and Baseline	Endovascular recanalisation			Discharge	Follow-up Visits		
		Pre-procedure	Intra-procedure	Post-procedure		30-Day (±7 days)	90-Day (±7 days)	1-Year (±30 days)
Inclusion/Exclusion	X	X						
Informed Consent	X							
Clinical Assessment, Vital Signs, and Physical Exam	X	X			X	X	X	X
Laboratory tests	X					X	X	X
NIHSS (blinded to treatment)	X				X	X		
mRS (blinded to treatment)	X				X	X	X	X
EQ-5D (blinded to treatment)						X	X	X
mTICI assessment		X	X	X				
CT/MRI	X			X			X	X
CTP/PWI	X						X	X
CTA/DSA	X						X	X
Protocol Deviations		X	X	X	X	X	X	X
Medication review and patient compliance survey	X	X	X	X	X	X	X	X
Primary and secondary outcomes			X	X	X	X	X	X

Figure 1. Study design and treatment grouping flowchart

1. Background

Intracranial large artery atherosclerotic stenosis or occlusion constitutes one of the major etiologies of ischemic stroke worldwide.^{1,2} Previous studies have showed that ischemic stroke among Asian populations, African Americans, and Hispanic populations are primarily attributable to intracranial large artery stenosis and occlusion.^{3,4} The Chinese Intracranial Atherosclerosis (CICAS) Study revealed that in the Chinese population, 33%-50% of ischemic strokes and over 50% of transient ischemic attacks (TIAs) were caused by intracranial artery stenosis or occlusion.⁵ Furthermore, patients with intracranial artery occlusion (IAO) exhibit higher mortality rates, stroke incidence, and recurrence rates.⁵ Beyond this, a series of studies have consistently demonstrated that the most common location for IAO is in the anterior circulation, with middle cerebral artery occlusion being the most prevalent, while in the posterior circulation, basilar artery occlusion is frequently observed.^{6,7}

Endovascular treatment (EVT) has been proven to be an effective treatment option within the established time window for acute ischemic stroke attributable to IAO.^{8,9,10,11,12} Additionally, the relevant clinical trials have collectively established the extension of the therapeutic window for EVT in acute IAO to 24 hours.^{13,14} However, a significant number of patients with acute ischemic stroke attributable to IAO frequently fail to achieve endovascular recanalisation (ER) during the acute phase due to delays in reaching a qualified stroke center in time after symptom onset.¹⁵ Consequently, these patients were compelled to transition into the non-acute phase. Currently, there is no definite definition for non-acute intracranial artery occlusion. To distinguish the therapeutic time window for acute occlusion, previous studies have defined occlusion with a duration exceeding 24 hours as non-acute occlusion.^{16,17} In patients with symptomatic non-acute intracranial artery occlusion (sNA-IAO), severe hemodynamic compromise resulting from chronic cerebral hypoperfusion has emerged as a significant contributor to both initial occurrence and recurrence of ischemic stroke, demonstrating strong correlation with adverse functional outcomes.^{1,18} Nevertheless, the optimal therapeutic approach for sNA-IAO beyond 24 hours after symptom onset continues to pose a significant clinical challenge.

Clinical experience suggests that for sNA-IAO patients presenting with significant clinical manifestations or experiencing symptom progression/recurrence despite receiving optimal medical management, ER or extracranial-intracranial (EC-IC) bypass surgery may be considered as therapeutic options. With respect to EC-IC bypass surgery, previous studies have failed to demonstrate superior efficacy compared to medical treatment in patients with symptomatic atherosclerotic large artery occlusion accompanied by severe hemodynamic compromise.^{19,20,21} Regrettably, large-scale prospective controlled studies specifically investigating the potential superiority of endovascular recanalization for patients with sNA-IAO remain scarce. Notably, a collection of case series reports and small retrospective analyses have demonstrated that ER for carefully selected sNA-IAO patients beyond the 24-hour window seems feasible and may represent a promising therapeutic option.^{16,17,22,23,24,25,26,27,28,29,30} Nonetheless, these studies were single arm, small sample size, retrospective studies. While ER may represent a potential therapeutic alternative for sNA-IAO patients refractory to medical treatment, there is a paucity of controlled studies establishing its definitive superiority over medical management. Furthermore, compared to EVT in acute IAO, recanalization procedures in non-acute cases are associated with elevated procedure-related risks and increased susceptibility to symptomatic intracranial hemorrhage, raising substantial safety concerns.

Consequently, We conducted a multicenter, prospective, cohort study to investigate whether ER combined with medical treatment is superior to medical treatment alone for sNA-IAO.

2. Study Objective

The primary objective of this study is to investigate whether ER plus medical treatment is superior to medical treatment alone for sNA-IAO in the primary outcome (any stroke or death within 30 days after enrollment or ischemic stroke in the territory of the qualifying artery beyond 30 days through 1 year after enrollment).

3. Methods

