3.2 Participants Selection and Enrollment

Patients eligible for initial study screening are those who present with occlusion in the intracranial internal carotid artery (ICA), M1 segment of middle cerebral artery (MCA), intracranial vertebral artery (VA) or basilar artery (BA), presenting beyond 24 hours of symptom onset. All such patients who meet all eligibility criteria as follows and with informed consent will be enrolled in the study.

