3.2.1 Inclusion criteria

Patient eligibility for study enrollment is determined based on the following inclusion criteria:

- (1) Age ranging between 18 and 80 years.
- (2) sNA-IAO defined as:
 - ① Time from latest ischemic event (ischemic stroke or TIA) in territory of the qualifying artery to enrollment is beyond 24 hours and within 90 days.
 - ② Occlusion of intracranial ICA, M1 segment of MCA, intracranial VA (with contralateral VA hypoplasia or occlusion) or BA confirmed by computed tomographic angiography (CTA) or digital subtraction angiography (DSA).
- (3) Computed tomographic (CT) or magnetic resonance imaging (MRI) demonstrating Alberta Stroke Program Early CT Score (ASPECTS) ≥ 6 (for anterior circulation) or Posterior Circulation Alberta Stroke Program Early CT Score (pc-ASPECTS) ≥ 6 and pons-midbrain index (PMI) < 3 (for posterior circulation).
- (4) Modified Rankin Scale (mRS) score 0-2 at the time of enrollment.
- (5) Technical feasibility of endovascular recanalization for the qualifying artery evaluated by two experienced interventional neuroradiologists.
- (6) More than one risk factor for atherosclerosis.

(7) Signed informed consent form.

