3.3 Participating Center Eligibility

To minimize selection bias, all participating centers are mandated to systematically enroll consecutive eligible patients according to predefined protocol criteria. To be fully eligible for participation in this study, participating centers selection are required to meet the following minimum criteria:(1) all study centers are required to have performed at least 120 endovascular procedures annually, including at least 40 cases of intracranial artery endovascular procedures; (2) the interventional neuroradiologists at these centers had each performed over 100 endovascular procedures..

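### Table 1 re-checks eligibility before the procedure in ER patients only, and the plan does not say what a failed check does to a patient's place in the analysis

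*Protocol*

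**What the plan says.** Protocol, Schedule of assessments, Table 1. The columns open with "Study Requirements Screening and Baseline Endovascular recanalisation", and Pre-procedure is the first sub-column under the ER heading. The eligibility row is "Inclusion/Exclusion X X". Its second mark therefore falls at a step that a medical-group patient does not have. Informed consent is marked only at screening and baseline.

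Protocol 3.2 describes a single entry decision: "All such patients who meet all eligibility criteria as follows and with informed consent will be enrolled in the study". Section 3.2.2 treats anyone meeting an exclusion criterion as ineligible to take part. Section 3.3 relies on consecutive entry as a safeguard: "To minimize selection bias, all participating centers are mandated to systematically enroll consecutive eligible patients according to predefined protocol criteria".

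On grouping, the protocol synopsis forms the groups by the treatment approach selected. Protocol 3.6 and SAP Section 4 form them by the treatment received.

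Protocol 3.9.1 counts the primary outcome from enrollment. SAP 7.3 lists deviations from the eligibility criteria. SAP 7.2 restricts the final analysis to patients who completed one year of follow-up.

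**The concern.** The schedule applies the entry criteria twice to patients heading for ER and once to everyone else, and the consequence of failing the second application is undefined. Suppose a patient chooses ER, is enrolled, and then has an intracranial hemorrhage or a myocardial infarction before the procedure. The hemorrhage and infarction exclusions in 3.2.2 are not worded as fixed at enrollment, so this patient could be judged ineligible and leave the cohort. If the patient stays in the cohort but is not treated, grouping by treatment received puts the patient in the medical group. A medical patient with the same event has no second check and stays where they are.

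Both routes remove post-enrollment bad outcomes from the ER group, and the second also adds them to the comparator. Propensity matching and Cox adjustment use baseline covariates, so neither can repair a selection that depends on what happened after enrollment. The consecutive-enrollment safeguard in 3.3 does not help either, because the selection would come after entry.

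**Working it through.** **What can happen to an ER chooser who fails the second check**

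- *Removed.* This follows if 3.2.2 is applied at that point. It would also follow in practice if the patient is withdrawn and does not complete the year, through the completer restriction in SAP 7.2.
- *Counted as medical.* This follows from Protocol 3.6 and SAP Section 4 if the patient stays in the cohort untreated.
- *Kept in the ER group.* This follows only from the synopsis wording on treatment selected, which 3.6 and the SAP contradict.

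**What could be newly found.** At Pre-procedure, clinical assessment is repeated ("Clinical Assessment, Vital Signs, and Physical Exam X X") and an angiographic grade is taken ("mTICI assessment X X X"). Laboratory tests, NIHSS, mRS, CT/MRI, CTP/PWI and CTA/DSA are not marked there. The scope for new failures is limited but not nil.

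**Size, by illustration.** The documents provided give no sample size, event rate or failure rate, so every input here is an assumption. Let p be the one-year risk in both groups (no true effect), f the share of ER choosers failing the check, and q the risk of those who fail. Take equal numbers of ER and medical choosers.

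- Risk left in the ER group: (p − f·q)/(1 − f)
- Medical risk if the failures are moved there: (p + f·q)/(1 + f)
- Hazard ratio: ln(1 − ER risk)/ln(1 − medical risk)

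With p = 15%, f = 3% and q = 30%:

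- ER risk = (0.15 − 0.009)/0.97 = 0.1454
- Medical risk if moved = (0.15 + 0.009)/1.03 = 0.1544
- HR if dropped = ln(0.8546)/ln(0.85) = 0.967
- HR if moved = ln(0.8546)/ln(0.8456) = 0.937

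The same formulas give, for p = 15% and f = 3%:

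| Risk of those failing (q) | ER risk left | Medical risk if moved | HR if dropped | HR if moved |
|---|---|---|---|---|
| 7.5% (half the average) | 15.23% | 14.78% | 1.02 | 1.03 |
| 15% (average) | 15.00% | 15.00% | 1.00 | 1.00 |
| 30% (double) | 14.54% | 15.44% | 0.97 | 0.94 |
| 100% (all have events) | 12.37% | 17.48% | 0.81 | 0.69 |

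Over p from 10% to 20% and f from 1% to 5%, double risk gives an HR of 0.94 to 0.99 if dropped and 0.89 to 0.98 if moved. The extreme case gives 0.51 to 0.96 and 0.35 to 0.91. If nobody fails, or if those who fail stay in the ER group, the HR is 1.00 whatever p and q are.

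**The case against.** The strongest reply is that no sentence in either document removes or transfers anyone for failing the second check. SAP 7.3 lists eligibility deviations and does not delete them, and the completer restriction applies to both groups. The study flowchart (Figure 1) is not available in the text reviewed, so it may deal with this step. All of that stands. A reader might infer from Table 1 that the ER group is in fact cleaned of bad outcomes. The documents do not support that; they only leave it possible.

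Four further inferences are tempting and should not be drawn.

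- *Worsening to an mRS above 2 would disqualify an ER patient.* The criterion is "Modified Rankin Scale (mRS) score 0-2 at the time of enrollment", so later worsening does not breach it.
- *The three days of antiplatelet therapy create a known waiting period.* Protocol 3.6.1 places them before the procedure and does not say that they follow enrollment.
- *ER patients are angiographically verified and medical patients are not.* Both groups enter on the same imaging criterion ("or BA confirmed by computed tomographic angiography (CTA) or digital subtraction angiography (DSA"). Sections 3.5 and 3.14 send all baseline imaging to a blinded core laboratory, and 3.6 has feasibility assessed in every patient.
- *A risk ratio near 0.8 is the likely size.* That needs every removed patient to have had a primary event. Failures for incidental findings would not fit, and removing lower-risk patients would push the estimate against ER.

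These points reduce the likely size. They do not supply the missing rule, and the conflict between the synopsis and Section 3.6 on how groups are formed remains. Table columns were read from PDF, so their positions carry a little uncertainty, but the two marks line up with the first two columns.

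**Conclusion.** The point holds as a gap in specification. The plan schedules an eligibility check in one group only, after what Section 3.2 presents as a single common decision, and gives no consistent rule that keeps an ER chooser who fails it in the ER group. Bias toward ER needs three things: some patients fail after enrollment, they are dropped or moved, and their prognosis is worse than average. The documents establish none of these and prevent none of them. Under the assumed 15% risk and 3% failing, the distortion is small at double risk (HR about 0.97 or 0.94) and becomes large only in the extreme case (about 0.81 or 0.69). It is worth correcting because the correction is cheap and no planned adjustment can undo the problem afterwards.

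**What to change.** - Keep the pre-procedure check, but relabel the Table 1 entry as one that does not affect study eligibility. Whether a procedure goes ahead is a clinical matter outside this point.
- State in Protocol 3.2 and in the SAP that eligibility is determined once, at enrollment, by the same criteria in both groups. State also that no enrolled patient is removed, or moved between groups, for a finding made after enrollment.
- Reconcile the synopsis, Protocol 3.6 and SAP Section 4 on how groups are formed. ER choosers who are not treated should stay in the group chosen at enrollment, at least in a sensitivity analysis, with their events counted from enrollment.
- Report, by group, the number of patients who did not receive the treatment they chose, with reasons.

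The cost is one table label, a few sentences and, at most, one sensitivity analysis. The downside is that a few untreated ER choosers remain in the ER group and slightly dilute any true effect.

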3.1 Study Design

The Endovascular Recanalization for Non-Acute Intracranial Artery Occlusion (ERNA-IAO) study is a multicenter, prospective, cohort study, this cohort prospectively will enroll consecutive patients with radiologically confirmed sNA-IAO at 6 comprehensive stroke centers in China from January 1,2020 to October 31, 2023. All participants or their legal representatives provide written informed consent before enrollment. The primary objective of this study is to evaluate whether ER plus medical treatment is superior to medical treatment alone for patients with sNA-IAO presenting beyond 24 hours after symptom onset. All study centers complied with the Expert Consensus on Standardized Diagnosis and Treatment in China, ensuring consistent data acquisition across sites. The study protocol was approved by the Institutional Ethics Committee of Beijing Tiantan Hospital (approval number: KY2020-114-02), and each subcenter, and will follow the Strengthening the Reporting of Observational Studies in Epidemiology (STROBE) guideline.

